2.7 Prior and Concomitant medication

The number and percentage of patients taking concomitant therapies will be summarized by preferred term according to the WHO Drug Reference List dictionary using the Safety Set. Summaries will be presented over two time periods, in separate tables: therapies received prior to the start of study treatment and therapies received after the start of study treatment. Categorisation of the time period will be determined based on recorded or imputed start and end dates of medications. Rules for imputing incomplete (start and end) dates are described in Section 2.4.3.3.

Medications will be presented in alphabetical order, by ATC codes and grouped by *anatomical main group* (the 1st level of the ATC codes). Tables will also show the overall number and percentage of subjects receiving at least one drug of a particular ATC code and at least one drug in a particular anatomical main group.

For both prior and concomitant medications, separate summaries will be provided for non-ocular, study eye, and fellow eye. Treatments that are specified as being taken in both eyes will be included in summaries for both the study eye and the fellow eye.

2.8 Efficacy evaluation

The primary objective is to evaluate the effectiveness of two treatment regimens by assessing the mean change in BCVA from baseline to Month 24 in each treatment group. A key secondary endpoint is to evaluate the effectiveness of two treatment regimens by assessing the mean change in BCVA from baseline to Month 12 in each treatment group. A mixed model (see below) utilising all data will be the primary analysis to assess both these endpoints in the one analysis with no imputation for missing data. Supportive and Sensitivity analyses will be conducted as described in Section 2.8.2.1.

Other key secondary variables include the central retina thickness and number of injections at Month 12 and Month 24.

2.8.1 Variables

The primary efficacy variable and key secondary variables are:

- Mean change in BCVA from baseline to month 24
- Mean change in BCVA from baseline to month 12
- Mean change in central retinal thickness from baseline to month 12 and month 24
- Number of injections from baseline to month 12 and 24

The additional secondary variables are:

- Mean change in area of new and existing geographic atrophy from baseline to month 12 and 24.

Patients at sites where autofluorescence can be undertaken will be assessed for the presence of geographic atrophy at Baseline, visit 4 (week 8) and then again at the 12 and 24 month visits. If present, the area of geographic atrophy will be estimated.

- New Geographic Atrophy at month 12 and month 24^a (Yes, No)
 - Change in area of geographic atrophy from the visit where geographic atrophy was first present
- Intra-retinal (IRF) and Sub-retinal fluid (SRF) (present/absent)

At each relevant assessment visit, the patient is examined for the presence/absence of IRF and SRF by the central reading centre as per the definitions for their treatment arm.

- The proportion of patients showing no IRF and SRF at month 2, 12 and 24
- Proportion of patients showing greater than or equal to 15 letters (EDTRS) gain and less than 15 letters loss from baseline to month 24.
- Proportion of patients with SRF as assessed by the [REDACTED] CRC and IRF as assessed by Investigators at baseline who do not resolve their SRF and IRF by Month 24

The remaining exploratory variables are:

- Proportion of patients with a) SRF, b) IRF, c) both SRF and IRF, d) neither SRF and/or IRF at baseline, month 2, 12 and 24
- Proportion of patients with $\geq 6/12$ visual acuity at baseline, month 12 and month 24
- Proportion of patients with 6/60 or worse visual acuity at baseline, month 12 and 24
- The proportion of patients with IRF and SRF at baseline who never resolve either their IRF or SRF at any visit up to Month 2, 12 and 24.
- Proportion of patients with SRF at baseline who never resolve their SRF at any visit up to Month 2, 12 and 24 (irrespective of their IRF)
- Proportion of patients with IRF at baseline who never resolve their IRF at any visit up to Month 2, 12 and 24 (irrespective of SRF)

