**Table 14.2-7 Interval Decision Summary Table**

Full Analysis Set

| Visit  | Interval Decision*                     | Intensive
(N=X) | Relaxed
(N=X) | Total
(N=X) |
|--------|--|--------------------|------------------|----------------|
| Week 8 |  |                    |                  |                |
|        | Loss in VA                             | x (xx.x)           | x (xx.x)         | x (xx.x)       |
|        | Haemorrhage                            | x (xx.x)           | x (xx.x)         | x (xx.x)       |
|        | IRF/SRF                                | x (xx.x)           | x (xx.x)         | x (xx.x)       |
|        | Loss in VA AND Haemorrhage             | x (xx.x)           | x (xx.x)         | x (xx.x)       |
|        | Loss in VA AND IRF/SRF                 | x (xx.x)           | x (xx.x)         | x (xx.x)       |
|        | Loss in VA AND Haemorrhage AND IRF/SRF | x (xx.x)           | x (xx.x)         | x (xx.x)       |
|        | Haemorrhage AND IRF/SRF                | x (xx.x)           | x (xx.x)         | x (xx.x)       |
| Week n | .....                                  |                    |                  |                |

\*Interval Decisions:

Loss in VA: A loss of VA of >=5 letters or more than the best VA recorded since treatment started (Where VA loss is considered, by the investigator, to be due to disease activity);

Haemorrhage: New retinal haemorrhage;

IRF/SRF: Intensive Arm: The presence of any intra-retinal fluid or sub-retinal fluid on OCT  
Relaxed Arm: The presence of any intra-retinal fluid or sub-retinal fluid >200 µm in height at foveal centre?

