**Listing 16.2.6-9 Optical Coherence Tomography (OCT) by treatment (STUDY EYE) (Central Reading Center Data)**

Full Analysis Set

| Subject Number             | Visit | STUDY eye assessed | Parameter                                    | Result | Comments |
|----------------------------|-------|--------------------|--|--------|----------|
| Intensive
XXX-XX | ABCD  | Left               | Central Subfield Foveal Thickness            | xx     | ABCD     |
|                            |       |                    | Central Subfield Volume                      | xx     |          |
|                            |       |                    | Cysts Present?                               | Yes    |          |
|                            |       |                    | Cyst(s) involving central macula             | Yes    |          |
|                            |       |                    | Cysts: Thickness at Center Point             | xx     |          |
|                            |       |                    | Vitreomacular traction present               | Yes    |          |
|                            | ..... |                    | Subretinal fluid (within 6x6mm scan) present | Yes    |          |
|                            |       |                    | Intraretinal fluid present                   | No     |          |
|                            |       |                    | Vitreoretinal Abnormalities                  | No     |          |
|                            |       |                    | Type of OCT                                  | HD     |          |
|                            |       |                    | GA Measurement*                              | xx     |          |
|                            |       |                    | Subfoveal SRF (at centrepoint) present**     | Yes    |          |
| .....                      |       |                    |  |        |          |
| Relaxed
.....    |       |                    |  |        |          |

\* Where allowable by imaging equipment at site

\*\* For the relaxed arm, if "Yes", height "> 200um" or "= or <200um"

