Table 2-1	Analysis set exclusion summary	8
Table 2.3-3	Study Assessment Windows	9
Table 2.7.2-1	Primary Efficacy Analyses.....	23
Table 2.7.2-2	Secondary Efficacy Analyses.....	23
Table 2.7.2-3	Exploratory Efficacy Analyses	23
Table 2.7.2.5-1	Mixed Models	26
Table 2.7.2.8-1	Logistic Regression Models.....	28

1 Introduction

[figure not shown]
Studies covered are listed in Table 1-1. The study design, objective, treatment duration, and efficacy variables for this indication may be different from other related studies due to different indications and phases of clinical development so that almost every study is unique. The main purpose is to provide project-level standards for the statistical analyses of efficacy and safety data which are common or similar across studies. This MAP can be used as a reference or guidance of statistical methods for future studies not listed in Table 1-1.

Table 1-1 Studies covered in the MAP

Indication /Study	Phase/ Duration	Treatment/ dose	Primary objective
AMD / RFB002	IV	(1) Intensive retinal fluid retreatment regimen (2) Relaxed retinal fluid retreatment regimen	To test the non-inferiority (visual acuity benefit that is not clinically worse) of intravitreal ranibizumab when administered to resolve IRF or SRF >200 µm under the fovea (relaxed retinal fluid management) relative to when administered to completely resolve both IRF and SRF (intensive retinal fluid management) in patients with wet AMD. The primary endpoint for the study will be the mean change in BCVA from baseline to month 24.

This is a randomised, multi-centre, non-inferiority trial investigating a relaxed fluid retreatment regimen relative to an intensive fluid retreatment regimen (using a non-inferiority margin of 5 letters on the primary endpoint of mean change in BCVA). After consenting to participate in the study, patients will participate in a screening period lasting up to 2 weeks to evaluate patient eligibility. After eligibility confirmation at the Baseline Visit, patients will be randomised in a 1:1 ratio to one of the two treatment arms i.e. intensive retinal fluid regimen or relaxed retinal fluid regimen within the appropriate stratum depending on the treatment at baseline for the non-study eye i.e. none, ranibizumab or other anti-VEGF therapy. Only one eye will be selected/treated as the study eye.

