2.1 General considerations

Descriptive statistics will include n (number of observations), mean, standard deviation, median, minimum and maximum for continuous variables, and frequencies and percentages for categorical variables.

The study eye is the eye identified by the investigator according to the protocol inclusion and exclusion criteria and recorded as such at the screening visit in the eCRF.

The efficacy analyses of this study will be based on the study eye data only.

For non-ocular, study eye, and fellow eye summary tables, figures, and listings will be based on all patients included in the analysis/set population under consideration. Unless otherwise specified, all confidence intervals (CIs) and p values will be two-sided and will be based on an alpha significance level of 0.05.

Central Reading Centre data will be used for efficacy summary tables and analyses, whilst all site and Central Reading Centre data will be included in listings.

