2.5.5 Baseline Characteristics

The following baseline characteristic variables will be analysed using the Randomised Set:

Categorical baseline variables (per eCRF):

- Study eye selection (L/R)
- Prior wet AMD treatment for fellow eye (Yes/No)
- Prior wet AMD treatment for fellow eye (Lucentis, Eylea, Visudyne, Avastin, Steroids, Other)
- Family history of AMD
- History of thromboembolic events
- Smoking history (as reported, as well as grouped with “Never smoked” and “Smoked in the past” combined)

Continuous baseline efficacy variables:

- Total BCVA score (per eCRF)
- OCT assessments (per [REDACTED]):
 - Central subfield foveal thickness (CSFT) (μm^2)
 - Central subfield volume (mm^3)
- FA assessments (per [REDACTED]):
 - Area of lesion (mm^2)
 - Area of CNV (mm^2)
 - Area of Geographic atrophy (mm^2)

Categorical baseline efficacy variables

- Visual acuity ≥ 70 letters (20/40) - per eCRF
- Visual acuity < 70 letters – per eCRF
- OCT assessments (per [REDACTED]):
 - Intra-retinal fluid (Present, Absent, Can't grade) (within 6x6mm scan) (also per eCRF)
 - Intra-retinal fluid centre involvement (Present, Absent, Can't grade)
 - Intra-retinal cysts (Present, Absent)
 - Intra-retinal cysts centre involvement (Present, Absent)
 - Sub-retinal fluid (Present, Absent, Can't grade) (within 6x6mm scan) (also per eCRF)
 - Sub-retinal fluid centre involvement (Present, Absent, Can't grade) (within 6x6mm scan)
 - Sub-retinal fluid at centrepoint (Present, Absent, Can't grade)
 - Sub-retinal fluid height at centrepoint ($> 200\mu\text{m}$, $\leq 200\mu\text{m}$, not applicable) (also per eCRF)
 - Morphologic changes (epiretinal membrane, vitreoretinal traction, macular hole, atrophy, other)
- FA assessments (per [REDACTED]):
 - CNV complex (lesion) (Absent, Definite, Questionable etc.) (also per eCRF)
 - CNV complex (lesion) location (subfoveal, juxtafoveal, extrafoveal, can't grade)
 - CNV complex (lesion) location (subfoveal, juxtafoveal, extrafoveal, can't grade), by presence of fluid central involvement
 - CNV location (subfoveal, juxtafoveal, extrafoveal, can't grade) (also per eCRF)
 - CNV location (subfoveal, juxtafoveal, extrafoveal, can't grade), by presence of fluid central involvement
 - CNV secondary to (AMD, angioid streaks, idiopathic, pathologic myopia, other)
 - Type of CNV (predominantly class, occult, fibrovascular PED, serous PED, other)
 - CNV leakage (Present, Absent)
 - Lesion components (CNV, blood, serous PED, RPE tear, can't grade, other)

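### SAP 2.8.1 grades fluid by each arm's own definition, which would code the same subretinal fluid as present in the intensive arm and absent in the relaxed arm

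*SAP*

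**What the plan says.** SAP 2.8.1 lists IRF and SRF (present/absent) as an additional secondary variable and has the patient examined at each relevant visit for "presence/absence of IRF and SRF by the central reading centre as per the definitions for their treatment arm". The next item is the proportion with no IRF and SRF at months 2, 12 and 24. SAP Table 2.8.2-2 assigns that endpoint to logistic regression, and model LR_6 in Table 2.8.2.8-1 has treatment as its only mandatory term. SAP 2.1 fixes the source: "Central Reading Centre data will be used for efficacy summary tables and analyses".

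SAP 2.8.1 does not say where the arm definitions are. The only ones supplied are in the footnote to shell Table 14.2-7 in the Protocol document. The intensive criterion reads "Intensive Arm: The presence of any intra-retinal fluid or sub-retinal fluid on OCT". The criterion for the other arm, where the height is in µm and taken at the foveal centre, reads "Relaxed Arm: The presence of any intra-retinal fluid or sub-retinal fluid >200".

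The primary objective in SAP Table 1-1 draws the same contrast: treatment for IRF or for SRF above 200 µm "under the fovea (relaxed retinal fluid management) relative to when administered to completely resolve both IRF and SRF".

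Other places use one SRF item for everyone. Listing 16.2.6-9 (reading-centre data) has "Subretinal fluid (within 6x6mm scan) present" with no arm condition; its relaxed-arm footnote attaches a height grade only to the separate centre-point item. SAP 2.5.5 lists SRF presence and SRF height as separate baseline variables for all patients. Shell Table 14.2-24 has one SRF label for both arms and no arm-specific footnote.

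**The concern.** A between-arm comparison needs the outcome measured the same way in both arms. Under the literal rule IRF is coded alike but SRF is not. An eye with SRF of 200 µm or less at the centre and no IRF counts as wet if randomised to intensive and dry if randomised to relaxed. The same holds for SRF of any height away from the foveal centre.

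That is the fluid the relaxed regimen is designed to tolerate, so the rule removes from the relaxed count what the fluid endpoints should reveal. It could produce a spurious drying advantage for relaxed or hide a real disadvantage. Because the listing and shells suggest a different coding, two programmers could also report different results from the same grades.

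**Working it through.** **Direction**

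| Eye | Coded, intensive | Coded, relaxed |
|---|---|---|
| Any IRF | present | present |
| SRF >200 µm at foveal centre | present | present |
| Only SRF ≤200 µm at centre, or only off-centre SRF | present | absent |
| No fluid | absent | absent |

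Only the third row differs. For LR_6 and for the SRF, both and neither proportions, the rule can therefore only lower the relaxed fluid count. Month 2 shows this most clearly. The legend to SAP Figure 1 gives both arms the same three initial 4-weekly treatments, so a systematic gap then would be expected from coding alone.

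For endpoints conditioned on baseline SRF (LR_3, LR_5/LR_7, LR_9, Table 14.2-25) the arms are not comparable. If baseline is graded alike and follow-up by arm, relaxed is favoured. If baseline is also graded by arm, the relaxed denominator holds only eyes above threshold and the direction is open. As an invented example, let 40% of above-threshold and 20% of sub-threshold SRF eyes never resolve, with above-threshold share t among SRF eyes. Intensive shows 20% + 20%·t, between 20% and 40%. If 10% of relaxed eyes stay above threshold throughout, relaxed looks better. If 35% do, relaxed looks worse whenever t < 0.75.

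**Number analysed**

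SAP 2.12 gives 165 per group for BCVA (margin 5, SD 15, no true difference, 80% power, 15% drop-out). A t-test at one-sided 0.025 needs 143 per arm, and 143 × 1.15 = 164.5, which rounds up to 165. After drop-out, 165 × 0.85 = 140.25, so I use 140 per arm.

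**Effect on LR_6**

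Assumptions, none given in the documents: no true difference; proportion of intensive eyes wet p = 0.30, 0.40, 0.50 or 0.60; share of eyes whose only fluid is sub-threshold SRF s = 0 to 0.10. Under the literal rule relaxed is recorded wet with probability p − s. The odds ratio for dry, relaxed versus intensive, is

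[(1 − p + s)/(p − s)] ÷ [(1 − p)/p].

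For p = 0.50 and s = 0.05 this is (0.55/0.45) ÷ (0.50/0.50) = 1.22. Rejection rates come from exact enumeration of the two binomials with a two-sided 5% Wald test on the log odds ratio, treatment only. Ranges are over p.

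| Share s | Odds ratio | Rejection rate |
|---|---|---|
| 0 (common definition) | 1.00 | 4.8–4.9% |
| 1% | 1.04–1.05 | 5.1–5.3% |
| 2% | 1.08–1.10 | 6.0–6.4% |
| 3% | 1.13–1.16 | 7.6–8.5% |
| 5% | 1.22–1.29 | 13–15% |
| 10% | 1.50–1.71 | 38–49% |

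Rejection reaches 10% at s = 3.6–4.0%, about 5 to 6 of 140 eyes. A normal-approximation two-proportion test over dry rates of 20–60% agrees: 13–17% at s = 5% and 39–49% at s = 10%.

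**Masking**

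Suppose relaxed is truly 10 points wetter, only through sub-threshold SRF (s = 0.10, intensive 30–50% wet). With a common definition the chance of a significant result against relaxed is 38–42%. Under the literal rule both arms are recorded equally wet and it falls to 2.4%.

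**The case against.** The strongest reply is that the arm rule was never meant to define the outcome. SAP 2.8.1 does not name its definitions. Table 14.2-7 is about interval decisions, and its visual-acuity item turns on investigator judgement. The clinical protocol that the SAP cites is not among the documents. Listing 16.2.6-9 shows what is arm-specific in the reading-centre data: an added height grade on the centre-point item, with overall SRF presence left neutral. Listing 16.2.6-7 likewise keeps presence and the 200 µm item in separate columns for both arms. Table 14.2-24 has screening rows, before any arm exists. No shell contains an arm-adjusted SRF variable, and the disagreement with Table 14.2-24 is one of silence.

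Much of this stands: a neutral item exists and may be what was intended. But it does not fit the words of 2.8.1, which apply the arm definitions to presence or absence itself, and no text makes the neutral item govern. If neutral coding was intended, the clause is wrong; if arm-specific coding was intended, the comparison is biased.

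It is also fair that the size is hypothetical and negligible at a 1% share. The example counts in shell Table 14.1-10 cannot settle it. They show 20 of 23 recorded centre-point heights at or below 200 µm, but centre-point status appears for only 69 of 347 eyes (34 + 12 + 23), and the same figures reappear under genotype headings in Table 14.1-11. I did not use them.

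**Conclusion.** The concern holds. As written, SAP 2.8.1 codes identical eyes differently by arm, and for LR_6 and the SRF, both and neither proportions the error can only favour relaxed. At a 5% share of affected eyes false rejection is about three times nominal; at 10% it is 38–49%. These figures rest on an assumed share and wet rate, 140 analysed per arm, and Table 14.2-7 supplying the arm definitions. For the never-resolve endpoints the arms are not comparable, and the direction depends on how baseline is graded.

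The reach is one additional secondary endpoint and several exploratory ones. The BCVA, CRT, injection and IRF-only endpoints are not affected. The SRF terms in MM_2 to MM_4 are optional and their source is not stated. This should be fixed; it does not threaten the primary conclusion.

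**What to change.** In SAP 2.8.1, delete the clause on treatment-arm definitions and state the following:

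- For every between-arm endpoint with an SRF component, at baseline and afterwards, SRF is present in either arm if the reading centre grades any subretinal fluid within the 6x6 mm scan.
- IRF keeps its existing source and definition for each endpoint, including the grouping with cysts where the outputs specify it, applied identically in both arms.
- Arm-specific thresholds are used only to describe interval decisions (Table 14.2-7).

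Code any SRF term used in MM_2 to MM_4 the same way. Footnote the SRF definition on Tables 14.2-24, 14.2-25, 14.2-27 and 14.2-28 and on Figures 14.2-14 to 14.2-16 and 14.2-19 to 14.2-21. Ask the reading centre to confirm that the 6x6 mm item was graded without regard to arm.

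The cost is one SAP paragraph, the footnotes and one query. If the item was graded neutrally, no images need re-grading; if it was graded by arm, that item needs re-reading for the relaxed arm. The sample size is unchanged. This concerns outcome coding only and alters no retreatment rule.

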**Figure 14.2-12 Proportion of of patients showing worse than 6/60 vision at Month 12 and 24**

[figure not shown]
Full Analysis Set

Column graph as per Figure 14.2-8.

**Figure 14.2-13** Proportion of patients with IRF and BCVA, over time by treatment

Full Analysis Set

**Note to Programmer:** "IRF" refers to IRF and IRC (cysts) grouped together

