2.8.2 Statistical hypothesis, model, and method of analysis

Statistical methodologies for efficacy variables are detailed in Table 2.8.2-1 (Primary efficacy), Table 2.8.2-2 (Secondary efficacy) and Table 2.8.2-3 (Exploratory efficacy).

Table 2.8.2-1 Primary and Key Secondary Efficacy Analyses

Study Endpoint	Method of Analysis
Mean change in BCVA from baseline to months 12 and 24	1. Mixed Modelling (Refer to Section 2.8.2.5) 2. Summary statistics of change from baseline will be presented.
Mean change in central retinal thickness (CRT) from baseline to months 12 and 24	1. Mixed Modelling (Refer to Section 2.8.2.5) 2. Summary statistics of change from baseline will be presented.
Mean number of injections from baseline to months 12 and 24	1. Binomial Model 2. All data will be listed.

Table 2.8.2-2 Additional Secondary Efficacy Analyses

Study Endpoint	Method of Analysis
Geographic Atrophy from Baseline to Month 12 / 24 (newly developed geographic atrophy between baseline and Month 24 (Yes/No))	1. Logistic regression model (Refer to Section 2.8.2.8) 2. Survival Analysis (Refer to Section 2.8.2.10)
Geographic Atrophy from Baseline to Month 12 / 24 (Change in area of geographic atrophy from the visit where geographic atrophy was first present)	1. Mixed Modelling (Refer to Section 2.8.2.8)
Proportion of patients showing greater than or equal to 15 letters (EDTRS) gain from baseline to month 24	1. Logistic regression model (Refer to Section 2.8.2.8)
Proportion of patients showing less than 15 letters loss from baseline to month 24	1. Logistic regression model (Refer to Section 2.8.2.8)
Proportion of patients showing no IRF and SRF at month 2, 12 and 24	1. Logistic regression model (Refer to Section 2.8.2.8)

Table 2.8.2-3 Exploratory Efficacy Analyses

Study Endpoint	Method of Analysis
Proportion of patients with SRF, as assessed by the █████ CRC, and IRF, as assessed by investigators at Baseline, who do not resolve their SRF and IRF by Month 24	1. Logistic regression model (Refer to Section 2.8.2.8)
The proportion of patients with a) SRF b) IRF c) both SRF and IRF d) neither SRF or IRF at baseline, 2, 12, 24 months	1. Logistic regression model (Refer to Section 2.8.2.8)

Proportion of patients with SRF at baseline who never resolve their SRF at any visit up to Month 2, 12 and 24 (irrespective of their IRF)	1. Logistic regression model (Refer to Section 2.8.2.8)

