2.8.2.8 Logistic regression

The logistic regression models to be fitted are detailed in Table 2.8.2.8-1.

Table 2.8.2.8-1 Logistic Regression Models

Model Number	Outcome Variable	Predictor/Covariate	
		Mandatory	Optional
LR_1	Newly developed geographic atrophy between baseline and Month 12 / 24 (Yes/No)	Treatment	Baseline geographic atrophy Baseline IRF/SRF Centre
LR_2	≥ 15 letter increase from baseline to month 24 (Yes/No)	Treatment	Baseline BCVA Centre
LR_3	SRF and IRF at baseline and never resolving SRF at any visit up to Month 2 (Yes/No) Same for Month 12 and 24	Treatment	Baseline IRF/SRF Centre
LR_4	Greater than or equal to 15 letters (EDTRS) gain and less than 15 letters loss from baseline to month 24	Treatment	Baseline BCVA Centre
LR_5	SRF as assessed by the ██████████ CRC and IRF as assessed by Investigators who do not resolve their SRF and IRF by Month 24	Treatment	Baseline IRF/SRF Centre
LR_6	No IRF and SRF at month 2, 12 and 24	Treatment	Baseline IRF/SRF Centre
LR_7	SRF (as assessed by the ██████████ CRC) and IRF (as assessed by Investigators) who do not resolve their SRF and IRF by Month 24	Treatment	Baseline IRF/SRF Centre
LR_8	IRF at baseline who never resolve their IRF at any visit up to Month 2, 12 and 24 (irrespective of SRF)	Treatment	Baseline IRF Centre

Model Number	Outcome Variable	Predictor/Covariate	
		Mandatory	Optional
LR_9	IRF and SRF at baseline who never resolve either their IRF or SRF at any visit up to Month 2, 12 and 24.	Treatment	Baseline IRF/SRF Centre
LR_10	Show $\geq 6/12$ visual acuity at baseline, Month 2, Month 12, month 24	Treatment	Baseline BCVA Centre
LR_11	Show 6/60 visual acuity or worse at baseline, Month 2, Month 12, month 24	Treatment	Baseline BCVA Centre

From each model the adjusted odds ratio for the outcome variable, for intensive compared with relaxed treatment, will be obtained with 2-sided 95% confidence limits.

Using PROC GENMOD to calculate the 95% confidence interval for the odds ratios assumes asymptotic normality of the Wald estimate for the regression coefficient. The 95% confidence interval for the regression parameter of the relaxed regime treatment effect relative to the intensive regime is calculated using an exponential transformation to create the 95% confidence interval for the odds ratio.

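### One fluid-resolution endpoint selects patients on reading-centre SRF and investigator IRF, against the SAP's own data-source rule, and does not say who grades resolution

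*SAP*

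**What the plan says.** SAP 2.1 sets the general rule: "Central Reading Centre data will be used for efficacy summary tables and analyses". Site data are to appear in the listings. For fluid at each relevant visit, SAP 2.8.1 repeats the idea, saying that "the patient is examined for the presence/absence of IRF and SRF by the central reading centre as per the definitions for their treatment arm".

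That section then lists, among the additional secondary variables, the proportion of patients with SRF graded by the "CRC and IRF as assessed by Investigators at baseline who do not resolve their SRF and IRF by Month 24". The mixed source recurs in two other places:

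- Table 2.8.2-3, under exploratory analyses, takes SRF from the reading centre "and IRF, as assessed by investigators at Baseline, who do not resolve their SRF and IRF by Month 24".
- Table 2.8.2.8-1 gives LR_5 as SRF by the "CRC and IRF as assessed by Investigators who do not resolve their SRF and IRF by Month 24". LR_7 is the same outcome again, with the same covariates. Neither row ties the grading to baseline.

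No section says who decides that either fluid has resolved. Both gradings are available by visit: Listing 16.2.6-7 carries the CRF OCT data and Listing 16.2.6-9 the reading-centre OCT data. The shells contain no table that names this mixed-grader endpoint. The nearest, Table 14.2-27, names no grader.

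**The concern.** A resolution endpoint compares a state at entry with a state at follow-up, so both should be read by the same grader to the same definition. Here IRF enters on the investigator's grade, and the grader at follow-up is left open between two options.

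- If follow-up IRF obeys SAP 2.1, the grader changes between entry and outcome. An eye that the investigator called positive and the reading centre called negative at baseline has its IRF component recorded as cleared with no change in the retina.
- If the investigator also grades follow-up, the grader is constant, but the efficacy result rests on site grading that SAP 2.1 sends to listings.

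Two programmers working from this SAP could therefore produce different results. The endpoint also has two tiers: additional secondary in 2.8.1 and exploratory in Table 2.8.2-3.

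**Working it through.** **Inputs.** These are the total-column counts in shell Table 14.1-10, N = 347. The IRF row without a source label is taken as reading-centre data, by contrast with the row marked as CRF data.

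| Baseline finding | Count | Share of 347 |
|---|---|---|
| IRF, reading centre | 130 | 37.5% |
| IRF, CRF (investigator) | 268 | 77.2% |
| IRF or intra-retinal cyst, reading centre | 214 | 61.7% |
| SRF, reading centre | 286 | 82.4% |
| SRF, CRF | 271 | 78.1% |

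The printed percentages reproduce, and the two columns add to the total in each row. Pearson chi-square without continuity correction also returns the printed p-values for the three IRF rows (0.7260, 0.4505 and 0.7266).

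**Which counts can be used.** Tables 14.1-10 (by treatment) and 14.1-11 (by genotype sample) carry the same 252/95 split and the same cell counts, so both sets of column labels cannot be right. Only totals are used below, and nothing is said about either arm.

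**Gap between graders in baseline IRF.**
- IRF alone: (268 − 130)/347 = 138/347 = 39.8 points.
- Cysts counted as IRF on the reading-centre side: (268 − 214)/347 = 54/347 = 15.6 points.
- For comparison, SRF: (286 − 271)/347 = 15/347 = 4.3 points.

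The second figure matters because the reading centre records cysts separately from IRF, while the programmer notes to the fluid figures (for example Figures 14.2-13 and 14.2-18) say that IRF "refers to IRF and IRC (cysts) grouped together". The documents do not say whether investigators counted cysts as IRF, so the range is 15.6 to 39.8 points.

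**Size of the endpoint population.** Entry needs reading-centre SRF (286) and investigator IRF (268). No cross-tabulation is given, so the overlap is bounded:
- minimum 286 + 268 − 347 = 207
- maximum min(286, 268) = 268

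**Share already IRF-negative at the reading centre at baseline.** If n eyes enter and at most k are reading-centre positive, at least (n − k)/n are negative. This rises with n, so the guaranteed minimum is at n = 207.
- IRF alone, k = 130: (207 − 130)/207 = 77/207 = 37%. At n = 268 it would be 138/268 = 51.5%.
- IRF or cyst, k = 214: 207 is below 214, so the minimum is 0. At n = 268 it would be 54/268 = 20.1%.

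**What this does to the outcome.** With reading-centre follow-up, these eyes have their IRF component cleared from the start. Read as requiring both fluids to clear, the endpoint still needs SRF to clear, and under SAP 2.1 one grader reads SRF throughout. The artefact removes one of two conditions; it does not by itself make a patient resolved.

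**After the fix (reading centre for both fluids).**
- IRF alone: 286 + 130 − 347 = 69, up to 130 eyes.
- IRF or cyst: 286 + 214 − 347 = 153, up to 214 eyes.

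**The case against.** The best defence is that the mixed source is deliberate. It recurs in 2.8.1, Table 2.8.2-3, LR_5 and LR_7, and the endpoint is not among those that SAP 3.1.3 says were added to the protocol, so it may come from the Clinical Study Protocol, which is cited but is not among these documents. That may be so. It would explain the entry rule, but the SAP would still need to state the exception to 2.1 and name the follow-up grader.

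Several stronger readings are tempting and are not supported:

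- **A 40-point disagreement between graders.** This holds only for the rows as labelled. Part of it may be definitional, and counting cysts reduces it to 15.6 points.
- **At least half of the group resolved by change of grader.** The 51.5% refers to all 268 investigator-positive eyes and ignores the SRF entry condition. The guaranteed minimum in the endpoint population is 37%, or zero with cysts, and SRF must still clear.
- **Investigators grade IRF by arm-specific criteria.** Table 14.2-7 gives "Intensive Arm: The presence of any intra-retinal fluid or sub-retinal fluid on OCT" for one arm, but the relaxed arm's criterion also includes any IRF. Only the SRF height rule differs, and SRF is the component assigned to the reading centre. Investigators probably know the arm, but no masking section is available to settle it.
- **The trial could not show whether fluid cleared.** Other endpoints cover absence of both fluids and never-resolving SRF, IRF or either, with no investigator grading specified.

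It is also fair that SAP 2.1 cannot be literal for every variable, since BCVA comes from the eCRF. For IRF, however, both gradings exist, and 2.8.1 names the reading centre.

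**Conclusion.** The concern holds in limited form. The endpoint's entry rule contradicts SAP 2.1 and the fluid statement in 2.8.1, the grader of resolution is not specified, the tier is inconsistent, and LR_5 and LR_7 are duplicates. These defects are in the text and depend on no figure.

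The possible distortion is confined to the IRF component and arises only if the reading centre grades follow-up. Its size rests on a baseline gap of 15.6 to 39.8 points. Among the 207 to 268 eyes entering, at least 37% are already reading-centre IRF-negative on IRF alone, with a guaranteed minimum of zero once cysts count. These figures assume that pre-filled shell totals are real data and that the unlabelled IRF row is the reading centre's. They show that a change of grader could matter; they do not show that any result was distorted or that one arm is favoured. The primary BCVA analysis is unaffected.

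**What to change.** Amend SAP 2.8.1, Table 2.8.2-3 and Table 2.8.2.8-1 as follows:

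1. Use reading-centre grades for both SRF and IRF, at baseline and at every follow-up visit.
2. Count IRF or intra-retinal cyst as IRF, matching the fluid figures and the variable already derived in Table 14.1-10. Say explicitly that resolution requires both fluids to clear, if that is the intention.
3. Present the investigator-graded version as description only. If the mixed entry rule is kept for a reason, state the reason as an exception to 2.1 and name the follow-up grader.
4. Give the endpoint one tier in both places.
5. Merge LR_5 and LR_7. If the redefined endpoint then duplicates LR_9, drop it.

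This needs wording and programming changes but no new data, because Listing 16.2.6-9 already carries reading-centre SRF, IRF and cysts by visit. The cost is a smaller eligible group, 153 to 214 eyes instead of 207 to 268, and so less precision for this one comparison.
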